6.0 Other Study Staff/Collaborators:

FirstName	LastName	Organization	Email	Role
There are no items to display				

7.0 * Type of Application:

- ☒ Clinical Research Proposal
- ☐ Expedited Retrospective Chart Review
- ☐ Request for Exemption
- ☐ New Registry
- ☐ Existing Approved Registry

Please click [here](#) to preview Exempt Categories.

Click [here](#) to preview Study Designs.

8.0 Select appropriate funding sources for this study:

Name
Other

Other Funding Sources:

Clinical and Translational Science Center

Note: If the funding source of the study is 'Industry Funded Support', Clinical Research Administration (CRA) will be

notified.

If your study requires CRA review, please upload applicable documents, including sponsor protocol, drug brochure, etc :

Name Version

There are no items to display

[Help](#)

ID: 2014-233

View: 1.1 CRP Information

[Help](#)

CRP Information

- 1.0 **The proposal should be submitted to the appropriate Clinical Review Panel (CRP) for scientific review. If you are unsure of which Clinical Review Panel to select, please contact [name] at [contact]**

*

Name

Rheumatology

[Help](#)

ID: 2014-233

View: 1.2 Regulatory Status of Drugs and Devices

[Help](#)

Regulatory Status of Drugs and Devices

- 1.0 **The regulatory status of the drugs or devices in this research proposal is:**

Name

Does not apply to this study

[Help](#)

ID: 2014-233

View: 1.3 Pharmacy Involvement / Impact to EPIC

[Help](#)

Pharmacy Involvement / Impact to EPIC

- 1.0 Is this an inpatient study?
☐ Yes ☒ No

- 2.0 * Will this study have Investigational Drug Service involvement?
(Pharmacy will be purchasing/dispensing any medications being used and/or study requires placebo and patient randomization)
☐ Yes ☒ No

3.0

If the answer to either question is yes, please explain briefly below AND contact [name] at [contact] ([contact]) or [name] at [contact] ([contact]).

[Help](#)

ID: 2014-233

View: 1.4 Study Locations

[Help](#)

Study Locations

1.0 Select the Research Facilities where this study will be conducted:

Facility

HSS

Other

1.1 If Other, please specify:

Hospital, medical offices, operating room, research building in the lab of [name]
3RD floor Caspary, Collaborative Research Center, Rockefeller University

2.0 * Is this a multi-Center study?

No

ID: 2014-233

View: 2 Specific Aims or Research Questions

This section will be reviewed by the appropriate Clinical Review Panel. Each of the headings in this section must be addressed.

[Help](#)

Specific Aims or Research Questions

1.0 What is the condition or intervention to be studied?

The condition to be studied is worsening (flare) of rheumatoid arthritis (RA) in patients who have undergone arthroplasty. RA patients undergoing arthroplasty most often have severe, erosive disease. If the rate of flare approaches the estimated 26% rate suggested in a previous study for RA patients after arthroplasty (*Johnson ACR 2011*), this could be of significance in regards to their long term arthroplasty and disease outcomes. Patients who flare may not be able to participate in the post-operative rehabilitation thought necessary for optimal arthroplasty outcomes, and it may be difficult for patients who flare after

*Please click
Here for
example.*

discontinuing immunosuppressant medications for surgery to regain remission or low disease activity. Detailed clinical data collected longitudinally from RA patients with severe erosive disease undergoing arthroplasty in conjunction with further characterization of the molecular profile of blood and operative tissue could provide valuable information to inform best practices for this patient group.

2.0 What is/are the research question(s)/specific aim(s)? Pose very specific questions that can be addressed within the proposed design of the study. Prioritize them in order of importance.

1. To determine the rate of post-operative RA flare within 6 weeks of surgery, defined as
 - a. Worsening of disease activity, defined as an increase in the DAS-28 by 1.2 or by 0.6 if the DAS28 was ≥ 3.2 , OR
 - b. Patient reported worsening, defined as noting they are worse or much worse on the question rating their RA since pre-surgery
 - c. AND one of:
 - i. patient wants/needs retreatment of DMARDs and/or biologics and/or prednisone increase (or Medrol dose pack or equivalent or intra-articular corticosteroid injection)
 - ii. increase in MD global of 2/10
 - iii. increase in patient global of 2/10 (on the OMERACT Preliminary Flare Questions [PFQ])
 - iv. flare severity score of ≥ 10
2. To evaluate the responsiveness of the OMERACT PFQ in patients who flare, as defined as a worsening of DAS-28 by 1.2 or by 0.6 if the DAS28 was ≥ 3.2 OR by patient reported worsening.
3. To determine predictors of post-operative flare within 6 weeks of surgery such as baseline disease activity measures and biomarkers, including molecules in the Rho associated kinase (ROCK) pathway, which are measures of immune system activation
4. a. To assess if variability in physical therapy milestones post-op is associated with flare at 6 weeks
 - b. To assess if variability in physical therapy milestones post-op is associated with patient reported outcome measures at 1 year (for e.g., HAQ, DAS-28, HOOS, KOOS).
5. To evaluate if RA patients who flared within 6 weeks after arthroplasty exhibit an increase in ROCK activation at 6 weeks over and above pre-operative baseline levels, compared with patients who don't flare.
6. To better understand the molecular signature of RA flare and prodrome to RA flare. Blood samples harvested during various states of RA disease activity will be analyzed by RNA sequencing and Luminex® protein array to establish which pathways fluctuate most during disease worsening as well as prodrome to worsening. RA flare and the prodrome to flare will be measured by patient self-report using validated instruments of patient reported prodromal symptoms, patient reported disease activity measures and the OMERACT PFQs.

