3.0 What is/are the hypothesis(es)?

1. 26% of RA patients will flare after TJR, defined as
 - a. Post op increases in DAS28 > 1.2 if baselines < 3.2 or > 0.6 if baseline ≥ 3.2 OR
 - b. Are worse or much worse on question rating their RA since pre-surgery AND
 - c. Have at least one of
 - i. Want / need treatment
 - ii. An increase in MD Global of 2/10
 - iii. An increase in Patient Global of 2/10 (according to the definitions noted above)
2. The OMERACT preliminary flare questions (PFQs) will detect patients who flare as defined above.
3. RA patients who flare after TJR have worse baseline pre-operative disease activity (DAS >3.2), worse baseline function (HOOS, KOOS, HAQ, elbow/shoulder surveys) and more likely will have had a history of withdrawing a biological therapy compared to patients who do not flare.
4. RA patients who flare post op will not meet their physical therapy milestones and will have worse HOOS, KOOS, elbow, or shoulder pain and function outcomes 1 year after arthroplasty.
5. RA patients who flare will exhibit enhanced immune activation when baseline levels are compared to levels in patients who flare within 6 weeks of surgery based on increased expression/activation of ROCK, IRF4, IRF5 and IRF8 and decreased expression/activity of their inhibitors (Def6 and SWAP-70). These molecules participate in a biologic pathway that regulates production of pro-inflammatory cytokines, potential mediators of RA flare.
6. There is a discrete set of genes expressed in circulating monocytes in RA patients during flare and prodrome of flare.

4.0 Identify and define the primary outcome and when the outcome will be measured. If measuring change in post-operative function is the most important, that will be your primary outcome.

The primary outcome is rate of RA flare within 6 weeks of surgery as measured by the OMERACT flare questionnaire.

5.0 Identify and define the secondary outcome(s) and when they will be measured (list additional goals one at a time with their corresponding outcomes).

1. The severity and impact of flares, using the OMERACT PFQs in the post arthroplasty setting: PFQs including flare intensity, duration of flare and worsening of domains associated with flare (pain, fatigue, stiffness, patient

- reported tender and swollen joint count, difficulties with coping and participation).
- 2. DAS28 at baseline and post-op week 6, and the change during this interval.

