If willing to participate, the RC will complete a study screening form, obtain consent, complete a Research Authorization Form and the patient will complete a pre-operative questionnaire/survey containing questions about their demographic information (race, ethnicity, age, weight), medical history, assessment of their replaced joint function, and symptoms as they relate to their RA (OA and IA patients will not be asked survey questions that apply only to RA patients). We requested an IRB approved Waiver of HIPAA Authorization.

o The questionnaire will include patient demographics, RA characteristics, co-morbid conditions, disease classification, medications, PtGA, SF-12, HAQ, RAPID, joint count homunculus, HOOS/KOOS/elbow/shoulder survey.

The research staff will complete a second survey that will ask about the participant's medical history, and medication history.

o The questionnaire will include Medications, disease duration and classification criteria, assessment for extra-articular disease and co-morbidities, MDGA, DAS28, CDAI

~~OA and IA~~ Patients: We will repeat both questionnaires at 6 weeks after surgery at the time of the participants' regularly scheduled appointment.

RA Patients only:

- We will repeat both questionnaires at 6 weeks and one year after surgery at the time of participants' regularly scheduled appointments.
- Questions about RA will also be asked by telephone or by e-mailing an electronic survey each week for six weeks, and then every three months for the rest of the year.

o The questionnaire will include OMERACT flare questions, RAPID, joint humunculus

All questionnaires can be completed in any of the following ways throughout the course of the study: in person at the hospital, over the phone, via e-mail using a secure survey, or by mailing paper forms to and from the hospital.

Blood sample:

We would like to collect and store serum from participants in this study, which means we will need to increase our day-of-surgery allowed blood draw limit from 50.5 to 56.6mL (well below the IRB cap of 550mL):

- **30mL** whole blood in green top heparin tubes (3 tubes, 10mL each, for PBMC isolation)
- **8.5mL** speckle top tube (1 tube, to be spun by research assistant and aliquotted for freezing at -80)
- **2.5mL** for PAXgene tubes (1 tube, to be frozen by the research assistant)
- If not ordered at Pre-Surgical Screening, **3mL** lavender top for erythrocyte sedimentation rate (as marker of inflammatory levels)

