Pending the distributions of the data, in aim 2 we will evaluate the standard mean difference or effect size for each domain (WOMAC, DAS-28, Flare questionnaire (pain, Pt global, stiffness, fatigue, coping, participation, Pt reported TJC, SJC) in patients who flare vs. those who do not based on criteria of DAS28 worsening, patient reported worsening, MD global, need to initiate or escalate treatment. We would also explore differences in long term WOMAC scores and biomarkers stratifying by flare and adjusting for unknown confounders including baseline function, age, sex, and co-morbidity score. Standard statistical tests will be used.

In aim 3 we will examine a limited number of predictors of flare within 6 weeks using appropriate statistical methods by using a generalized estimating equation and will adjust for unrecognized confounders/effect modifiers including long term WOMAC scores, baseline function, age, sex, and co-morbidity score, and biomarkers stratifying by flare. Standard statistical tests will be used.

In aim 4 we aim to determine how patients who flare meet physical therapy milestones including walking distance, and ADLs, in comparison to patients who do not flare. The evaluation of meeting physical therapy milestones is exploratory. Physical therapy milestones are routinely evaluated as post-op TJA measures and are done weekly. We will examine the distributions of change for each covariate recorded by physical therapy and compare changes in each domain stratified by flare vs. no-flare.

A potential analytic plan depending on distribution of the final data to assess PT milestones will include:

Physical therapy milestones will be assessed based on the questionnaire and analyzed as outlined below: patient VAS: continuous variable- ranging from 0 ~100, analyzed with T-test or regression

Change will be analyzed by

- 1- ANCOVA and study of change
- 2- GEE and treat delta as our continuous outcome

Walking distance: Ordinal variable - Chi-square, fisher exact

Stairs/Transfers/Activities/Driving/Employed: Nominal- Chi-square, fisher exact

We will also explore whether or not the meeting of PT milestones impacts pain and function at 1 year using the HOOS/KOOS. We will treat PT milestones as a binary and WOMAC outcomes will be analyzed as predictors.

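### No pre-operative OMERACT PFQ is listed, so PFQ change from before surgery, which Aim 2, secondary outcome 1 and flare criterion c.iii rely on, has no reference value on the instrument

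*Combined protocol and SAP*

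**What the plan says.** **What is to be measured.** Section 2, item 2.0, Aim 2 is "To evaluate the responsiveness of the OMERACT PFQ in patients who flare", with flare defined by DAS28 worsening or by patient-reported worsening. Secondary outcome 1 (item 5.0) covers "PFQs including flare intensity, duration of flare and worsening of domains associated with flare". Criterion c.iii of the Aim 1 flare definition is an "increase in patient global of 2/10 (on the OMERACT Preliminary Flare Questions [PFQ"). Each of these implies an earlier value. The flare anchors start before surgery: the DAS28 increase is judged against baseline, and the patient rates RA relative to the pre-surgery state.

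**What is scheduled.** Section 2.6 (Interventions and Observations) gives the pre-operative patient questionnaire as follows: "The questionnaire will include patient demographics, RA characteristics, co-morbid conditions, disease classification, medications, PtGA, SF-12, HAQ, RAPID, joint count homunculus, HOOS/KOOS/elbow/shoulder survey". The second questionnaire, completed by research staff, includes "assessment for extra-articular disease and co-morbidities, MDGA, DAS28, CDAI". Neither names the PFQ. For RA patients these two are repeated at 6 weeks and 1 year. A separate telephone or e-mail survey runs weekly for six weeks and then every three months, and here the text says "The questionnaire will include OMERACT flare questions, RAPID, joint humunculus". In section 2.7 (Data Collection) the PFQ is items 1-9 of the Participant Survey. The intake and office-visit forms do not list it.

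**What is planned.** Section 2.11.1, item 3.0 (Data Analysis) says that "in aim 2 we will evaluate the standard mean difference or effect size for each domain", comparing patients who flare with those who do not. It does not say whether the score is a post-operative level or a change. Adjustment for baseline function appears in the next sentence, on long-term WOMAC scores and biomarkers.

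**The concern.** Responsiveness is the ability of an instrument to move when the patient's state moves. It has to be measured over the interval on which the external anchor is defined, and here that interval begins before surgery. Without a pre-operative PFQ, the only contrast covering the whole instrument over that interval is one of post-operative levels.

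A contrast of levels mixes two things: whether the PFQ moved with flare, and whether flarers were already worse. Hypothesis 3 predicts the second, since flarers are expected to have worse disease activity and function before surgery. A post-operative difference could then favour the PFQ even if it did not respond to flare at all. The section on gaps in knowledge (2.1, item 3.0) says the study will validate a tool for identifying flare, so this ambiguity bears on a stated purpose. A baseline not collected before surgery cannot be recovered afterwards.

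**Working it through.** **1. The plan's own figure.** No sample size or power is stated for Aim 2. The primary-outcome calculation reproduces: with N = 47, P0 = 0.26 and P1 = 0.10, the exact two-sided test rejects at 6 or fewer or 19 or more flares, giving alpha 0.0445 and power 0.8143. It supplies the group sizes below but does not otherwise bear on this point.

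**2. Domains against the listed pre-operative content.**

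| PFQ domain | Pre-operative counterpart listed |
|---|---|
| Pain | RAPID (pain item) |
| Patient global | PtGA, RAPID |
| Patient-reported tender and swollen joints | Joint homunculus |
| Stiffness, fatigue | On the participant office-visit form; pre-operative use not stated |
| Coping, participation | None named |

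The counterparts are proxies. They come from other instruments, and the documents do not show that their scales match the PFQ items.

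**3. Group sizes.** 0.26 × 47 = 12.2, so about 12 flarers and 35 non-flarers.

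**4. Standard error of a standardised mean difference.** √(1/12 + 1/35) = 0.3345 (normal approximation, unit SD).

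**5. Carry-over when the PFQ does not respond to flare.** Let d0 be the baseline gap in SD units and r the pre/post correlation, with equal SDs before and after. The documents give neither, so both are assumptions. The gap in post-operative level is r × d0, or d0 if it carries over in full. The chance of a significant result is P(Z > 1.96 − d/0.3345) + P(Z < −1.96 − d/0.3345).

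| Assumed d0 | Carry-over | Spurious effect d (SD) | d/0.3345 | Significant at 5% |
|---|---|---|---|---|
| 0.5 | r = 0.3 | 0.15 | 0.45 | about 7% |
| 0.5 | r = 0.5 | 0.25 | 0.75 | about 12% |
| 0.5 | r = 0.7 | 0.35 | 1.05 | about 18% |
| 0.5 | full | 0.50 | 1.49 | about 32% |
| 0.3 | r = 0.3 | 0.09 | 0.27 | about 6% |
| 0.3 | full | 0.30 | 0.90 | about 15% |
| 0.8 | r = 0.7 | 0.56 | 1.67 | about 39% |
| 0.8 | full | 0.80 | 2.39 | about 67% |

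**6. Why a raw change score is not a complete answer.** Under the same model the between-group difference in raw change is r × d0 − d0 = −(1 − r) × d0. With d0 = 0.5 this is −0.35 SD at r = 0.3 and −0.15 SD at r = 0.7. Flarers would appear to improve relative to non-flarers through regression to the mean. Raw change is unbiased here only when the gap carries over in full. Adjusting for baseline removes r × d0 under this model.

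**7. Precision.** The effect detectable with 80% power at these sizes is (1.96 + 0.84) × 0.3345 = 0.94 SD, so the aim can be descriptive only.

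**The case against.** The strongest reply is that absence from the printed lists does not prove absence in practice. The intake form in section 2.7 also omits the HAQ, SF-12 and RAPID, all of which section 2.6 collects before surgery, so that form is not the full pre-operative set. Among the listed forms, RAPID3 appears only on the Participant Survey, which also holds the PFQ. If that form is used to collect RAPID before surgery, the PFQ may be collected with it. Item 3.0 of section 2.7 refers to attached forms that are not in the text, and criterion c.iii presupposes an earlier PFQ value. This stands as a reason for caution: an unlisted baseline PFQ cannot be excluded. It does not change what the written schedule says.

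A reader might infer that PFQ change cannot be scored for any patient. The documents do not support that. The PFQ is repeated weekly, so a patient who flares at week 4 has earlier post-operative values on the same instrument, and some domains have pre-operative proxies. Post-operative weeks do not replace the missing reference, however. Week 1 follows surgery and, per section 2.1, the usual withholding of medication, and a patient may already be flaring by then.

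A reader might also infer that the planned effect size is confounded by baseline severity. That goes too far, because the analysis text does not say level or change. The concern is conditional on levels being used.

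Hypothesis 2 asks whether the PFQ detects flare, and a comparison of scores by flare status is relevant evidence on that. Flare intensity and duration are not defined as changes from baseline either. Both points stand, but detection is not the responsiveness that Aim 2 names.

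**Conclusion.** The point holds in a limited form. Followed as written, the schedule provides no pre-surgery PFQ value, while Aim 2, secondary outcome 1 and criterion c.iii refer to change, and the anchors run from before surgery. Coping and participation have no named pre-operative item on any instrument.

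If the Aim 2 effect size is computed on post-operative levels, it carries baseline severity in the direction hypothesis 3 predicts. The size cannot be fixed from the documents. For an assumed 0.5 SD gap it is 0.15 to 0.35 SD at correlations of 0.3 to 0.7 (about 7% to 18% of studies significant) and 0.5 SD (about 32%) with full carry-over. The 32% figure is the upper end for that gap, not an expected rate.

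It would be tempting to conclude that the primary endpoint cannot be ascertained because c.iii is affected. That does not follow: c.iii is one of four alternatives under part c, and patient global is collected at baseline outside the PFQ. All secondary outcomes are declared exploratory and Aim 2 carries no power claim, so this is a change the plan should make rather than one on which the study depends.

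**What to change.** 1. In section 2.6, add the nine-item PFQ to the pre-operative questionnaire for RA patients. If the attached forms already give it before surgery, list it there.
2. Name pre-surgery as the reference time point for Aim 2, secondary outcome 1 and flare criterion c.iii.
3. In the aim 2 paragraph of Data Analysis (section 2.11.1), specify for each PFQ domain the standardised response mean within flarers and the flare versus non-flare difference adjusted for the baseline PFQ value (ANCOVA).
4. For patients enrolled without a baseline PFQ, limit change analyses to domains with a pre-operative item on the same scale, and report coping and participation as post-operative levels only.

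The cost is nine more items on a questionnaire that RA patients already complete, and a few sentences of analysis text. The drawback is a dataset in which patients already enrolled may lack the baseline. The documents do not say how many that is, so the number should be reported with the results.

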- 3. RAPID 3 weekly for 6 weeks and every 3 months for 1 year after arthroplasty, DAS-28, HOOS, KOOS, shoulder/elbow survey, patient global at baseline, 6 weeks, and 1 year.
- 4. Physical therapy functional milestones (PT questionnaire) at baseline and weekly for 86 weeks.
- 5. Biological markers of immune activation including levels of IRF4, IRF5, IRF8, IBP/Def6, SWAP-70, ROCK1, ROCK2 in synovial tissue taken at surgery. Levels of the same immune biomarkers in the peripheral blood measured pre-operatively, at 6 weeks post-operatively and at one year post-operatively.
- 6. Measurement of discrete set of genes expressed in circulating monocytes in RA patients obtained at baseline and weekly for 6 weeks after surgery in a subset of patients at high risk for flare (based on patients who withdrew biologics)

[Help](#)

ID: 2014-233

View: 2.1 Background

[Help](#)

BACKGROUND - Be sure to answer each question individually

1.0 Explain why these research questions are being asked:

RA patients who undergo arthroplasty have severe erosive disease; preliminary data suggests a flare rate as high as 26% in the post-operative period. This study would confirm the rate of post-operative flare, and evaluate the clinical and biologic factors which predict flare. We would also look at the impact of flare on arthroplasty outcomes (HOOS, KOOS, elbow/shoulder survey) and RA disease status (HAQ, DAS-28, RAPID) and better understand the biology of flare.

Flare after arthroplasty is clinically relevant, as medications are typically withheld at the time of surgery with the aim of diminishing surgical site infections.

However, patients who flare may not be able to adhere to post-operative rehabilitation regimens, leading to worse functional outcomes. In addition, patients who flare may have difficulty achieving remission or low disease activity when medications are re-started, leading to worse disease outcomes. There is little information about the characteristics and outcome of flare in the post-operative period. Better understanding of the incidence and clinical characteristics of post-operative flare and the means to predict who will be most likely to flare could lead to more tailored management strategies and potentially better arthroplasty and disease outcomes.

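### Aim 4a's flare window and direction do not match Hypothesis 4 and the analysis text, and the fixed flare/no-flare split of weekly milestones counts pre-flare weeks as flare weeks (minor; exploratory aim)

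*Combined protocol and SAP*

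**What the plan says.** **Aims (Specific Aims, item 2.0).** Aim 4a: "To assess if variability in physical therapy milestones post-op is associated with flare at 6 weeks". Aim 4b has the same form with a later endpoint: "To assess if variability in physical therapy milestones post-op is associated with patient reported outcome measures at 1 year". Aim 1 sets the cumulative window: "To determine the rate of post-operative RA flare within 6 weeks of surgery, defined as". Aims 3 and 5 use the same window.

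**Primary outcome (item 4.0).** "The primary outcome is rate of RA flare within 6 weeks of surgery as measured by the OMERACT flare questionnaire".

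**Hypothesis 4 (item 3.0).** "RA patients who flare post op will not meet their physical therapy milestones". The Background (item 1.0) gives the reasoning: "patients who flare may not be able to adhere to post-operative rehabilitation regimens, leading to worse functional outcomes".

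**Data Analysis (View 2.11.1, item 3.0), aim 4.** The stated purpose is to "determine how patients who flare meet physical therapy milestones including walking distance" and to "compare changes in each domain stratified by flare vs. no-flare". Named methods are a t-test or regression for a patient VAS, ANCOVA or GEE for change, and chi-square or Fisher tests for the ordinal and nominal milestones. The section calls the evaluation exploratory and the analytic plan potential.

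**Timing of the data.** The Data Analysis text says milestones are assessed weekly. RA patients answer the OMERACT flare questions weekly for six weeks (View 2.6). Within the flare window, DAS28 is measured only at baseline and week 6 (Specific Aims, item 5.0).

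**The concern.** There are two separate problems.

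**Wording.** Flare *at* 6 weeks is naturally read as flare present at that visit. Flare *within* 6 weeks is any flare up to then. A patient who flared in week 2 and recovered is a non-flarer under the first and a flarer under the second. Aim 4a also leaves open whether milestones are studied ahead of flare or flare ahead of milestones. That choice decides which weeks are informative: those before onset, or those from onset onward.

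**Analysis.** A fixed label on weekly data ignores when the flare began. No section gives an onset date, a lag, a rule for milestones recorded before the flare, or a flare term that changes over time. If flare impairs rehabilitation, as the Background proposes, its effect cannot appear in weeks before it starts. Averaging those weeks in blurs the contrast. If patients who will flare are already progressing more slowly, the same split reports that earlier deficit as an effect of flare.

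**Working it through.** **1. The plan's own figure.** The only powered quantity is the primary outcome: an exact two-sided binomial test of 0.26 against 0.10. With N = 47 and at most 0.025 in each tail, the test rejects at 6 or fewer or 19 or more flares. Alpha is 0.0445 and power 0.8143, as the plan states. The rows for N = 109 and N = 394 also reproduce. This point does not touch them.

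**2. Size of the flare group.** 47 × 0.26 = 12.2, so about 12 flarers and 35 non-flarers.

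**3. Share of flare-group weeks that precede onset.** Assume onset in week *k* (1 to 6) with probability w_k, and all six weeks weighted equally. Onset in week *k* leaves *k* − 1 earlier weeks, so the share is π = Σ w_k (k − 1) / 6. The onset patterns are assumptions.

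| Assumed onset | Calculation | π | Effect kept, 1 − π |
|---|---|---|---|
| All in week 1 | 0 / 6 | 0% | 100% |
| Front-loaded, 6:5:4:3:2:1 | (35/21) / 6 | 28% | 72% |
| Even | (15/6) / 6 = 15/36 | 42% | 58% |
| Back-loaded, 1:2:3:4:5:6 | (70/21) / 6 | 56% | 44% |

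These shares do not depend on N.

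**4. Dilution (illustrative).** Assume a continuous milestone, a true drop of 0.8 SD from onset onward, no deficit before onset, and within-patient correlation 0.5. The six-week mean has SD √[(1 + 5 × 0.5)/6] = 0.764. The standard error factor is √(1/12 + 1/35) = 0.3345. Approximate power of the fixed split is Φ[0.8(1 − π)/(0.764 × 0.3345) − 1.96].

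| Onset | Expected estimate | Power |
|---|---|---|
| All in week 1 | 0.80 SD | 88% |
| Front-loaded | 0.58 SD | 62% |
| Even | 0.47 SD | 45% |
| Back-loaded | 0.36 SD | 28% |

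Simulation agrees. With even onset the split gives 0.47 to 0.48 SD with 42% to 46% power. A time-varying flare term gives 0.80 to 0.82 SD, with 82% to 83% power in a plain regression and about 98% in an exchangeable GEE. If half of the 12 flares can be dated only to week 6, the plain regression's power falls to about 71%.

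**5. Inflation.** Let δ0 be a deficit already present in flarers before onset, after allowing for baseline, and δ1 the added effect of flare. The split estimates δ0 + (1 − π)δ1. It exceeds δ1 when δ0 > πδ1. With even onset and δ1 = 0.8 SD, the break-even is 0.417 × 0.8 = 0.33 SD. The plan gives reason to expect some δ0: Hypothesis 3 predicts worse baseline function in flarers, and Aim 6 studies a prodrome.

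**6. Can onset be dated, and are milestones weekly?** The patient-reported route to flare can be dated from the weekly questions. The DAS28 route cannot be dated before week 6. The weekly Participant Survey (View 2.7) lists only whether physical therapy was had or missed. Secondary outcome 4 and the Data Analysis text describe weekly milestones such as walking distance and stairs. Secondary outcome 4 also prints a duration of 86 weeks, longer than the one-year follow-up, possibly an editing remnant.

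**The case against.** **Aim 4a need not conflict in direction.** A reader might infer that Aim 4a makes flare the outcome while Hypothesis 4 makes it the cause. The documents do not go that far. An association is symmetric, and Hypothesis 4 uses no causal word. The parallel with Aim 4b suggests that milestones come first, but that is a reading. What stands is that Aim 4a states no direction and the analysis text follows Hypothesis 4.

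**No week-6 grouping is planned.** A reader might also infer that only flares present at week 6 would count, leaving very few flarers. No section plans that comparison; the analysis groups simply by flare or no flare. On this part a wording correction is enough.

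**The split need not dilute.** It is tempting to say that it must. It does not if all flares start in week 1, or if change is taken only from baseline to week 6, when every flare within the window has begun. With a pre-onset deficit it can inflate instead. The plan does not say which weeks enter the change, but it stresses weekly assessment and names a repeated-measures method.

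**The aim is exploratory and the plan provisional.** True, and GEE could carry a time-varying term. None is specified, however, and the text names only the change as outcome. This limits the severity but does not remove the point.

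**The size rests on assumptions.** Also true. Onset, effect and correlation are all assumed, and SD effects apply only to the continuous VAS, not to walking distance, stairs, transfers or driving.

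**Conclusion.** The point holds as a minor one. Aim 4a's window differs from that of Aims 1, 3 and 5 and the primary outcome, and its wording is not aligned with Hypothesis 4 and the analysis text. Applied across weeks 1 to 6, the fixed flare/no-flare split attributes pre-onset weeks to flare. The share is 28% to 56% under the spread-out onset patterns tried, 42% if even, and none if all flares begin in week 1. The sign of the resulting bias is not known in advance. The effect-size and power figures are illustrative only, because the documents give no onset distribution, milestone SD, correlation or effect. The primary outcome and its sample size are unaffected.

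**What to change.** 1. Reword Aim 4a to flare within 6 weeks, and state the Hypothesis 4 direction: flare as exposure, milestone as outcome.
2. In the GEE already named, regress each week's milestone on a time-varying indicator that flare has begun by that week. Date onset from the weekly OMERACT and patient-reported questions. Include week as a factor and the baseline milestone as a covariate, with a link suited to each milestone's type (continuous, ordinal or nominal).
3. Date flares met only through DAS28 to week 6, with a sensitivity analysis excluding them.
4. The indicator in step 2 never switches off, so add a sensitivity analysis using flare currently present.
5. Keep the flare/no-flare comparison as secondary, and state which weeks enter it.
6. Reconcile the weekly Participant Survey with secondary outcome 4 and the Data Analysis text on which milestones are recorded weekly and for how long. Where only therapy attendance is weekly, apply the model to attendance.

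**Cost.** A wording change and a little more programming. Weekly flare data are already planned, so no new visits are needed. The main limitation is less precise onset dating for DAS28-only flares. If milestones are not in fact recorded weekly, the model can address attendance only.
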